10. SAMPLE SIZE AND STATISTICAL ANALYSIS

Data will be reported quantitatively. All analyses will be performed from the intention-to-treat principle. Missing data will be dealt with by multiple imputation using the mice package in R.

a. Sample size calculation

The study in the United States will include at least three sites: Houston (BCM and MD Anderson Cancer Center considered as 'one site' due to proximity), Texas A&M University (TAMU), and Cedars Sinai Medical Center (CSMC). TAMU will enroll 1400 individuals. The proposed enrollment sample size is designed to provide 80% power to detect a 60% vaccine efficacy (a relative risk of 0.4 among the vaccinated). This is based on the observed three-fold decline in respiratory infections in the South Africa adolescent cohort with 80% power and 0.05 type 1 error in a two-tailed test. We expect 5% of study participants to develop symptomatic COVID19 during follow-up, therefore a sample size of 1400, with 700 receiving intervention and 700 receiving placebo. We do not expect significant loss to follow up among HCWs (there has been zero LTF after the first 500 participants). We will plot Kaplan-Meier curves comparing COVID19 disease between the BCG and placebo groups and report hazard ratios and p-values using Cox proportional hazard models. DBS samples will be collected at baseline and weeks 4, 8, 12, 16, 20 and 24 post intervention. PBMCs and plasma donations are optional at baseline, 12 and 24 weeks. If interim analysis identifies a large proportion of participants to be seropositive before intervention, power analysis will be evaluated and an amendment will be submitted if additional participants need to be recruited.

b. Interim analysis

One month after the first 100 participants are enrolled, an interim analysis will be held by the independent statistician of the trial. Data will be exported independently from all sites and then data collated and merged for the interim analysis). The above described statistical analysis will be evaluated as well as safety profile. Enrollment is expected to occur within the first two months of launch. Interim analysis will occur based on study enrollment and three to six interim analysis will occur based on temporal dynamics of enrollment as requested by the DSMB. We will stop the clinical trial early if the p-value of any interim analysis is smaller than the pre-specified type-1 error cutoff. Each interim analyses will be reported to the DSMB.

c. Primary study parameter(s)

The primary endpoint, development of COVID19 infection, we will use the Cox proportional-hazards model to calculate hazard ratios for the development of Covid-19. This will be reported as the proportion of individuals receiving the intervention who are PCR-positive or seroconvert.

d. Secondary study parameter(s)

Disease severity as discussed above and based on guidelines proposed by the World Health Organization. We will use the Chi square for significance to calculate the risk ratios for the development of severe Covid-19 disease. Disease severity will be based on the level of care required for individuals who test positive for COVID19 as follows: non-hospital-based care; patient hospitalized but no oxygen required; hospitalized and oxygen required; patient treated in intensive care and/or on mechanical ventilation; patient died. Additional WHO criteria for severity include severe pneumonia, respiratory failure, acute respiratory distress syndrome, sepsis and septic shock. Days absent will also be self-reported via the RedCap Research App. Immunology and epigenetic studies for innate training be implemented, but in brief, immune cells will be stimulated with non-specific (LPS, mitogen, BCG) and COVID19-specific antigens with immune function measured by ELISA and flow cytometry. Epigenetic studies are discussed in more detail below.

e. Other study parameters

Continuous baseline characteristics will be reported as mean and standard deviation or median and inter-quartile range, as appropriate. Categorical baseline characteristics will be reported as count and percentage. No statistical testing for baseline characteristics will be performed.

f. Synthesis

In this trial, the BCG vaccine will be used in hospital personnel during the epidemics to prevent infection with the new SARS-CoV-2 virus. The risk of the BCG vaccine is very well known (see product inserts) and only minor local side effects (redness, local pain) are common. The benefits of BCG vaccination based on earlier clinical studies are expected to be a reduction in infection and morbidity of at least 25% compared to unvaccinated individuals, and potentially much higher. These effects are mediated by the capacity of BCG to induce trained immunity and may represent an important tool for protection against SARS-CoV-2 virus infection until a specific effective vaccine is developed.

g. Epigenetic and Immune Corollary Studies

COVID19 serology is currently being developed. When available (FDA approved test availability is rapidly evolving and improving), serology from blood drawn at baseline will be used to exclude individuals with preceding COVID19 infection from analysis.

To evaluate if the metabolic-epigenetic-immune mechanisms of the non-specific benefits of BCG for Covid19 are similar to that as previously described (Arts et al 2017), the collection of 12 mL of blood, in sodium heparin tubes, will be option to the participant. Blood will be processed for plasma (~4mL) and PBMCs. PBMCs will be cryopreserved and saved for future epigenetic (ATAC-seq, ChIP-seq, DNA methyl EPIC) and immune functional studies.

h. Flow cytometry based immune profiling

A secondary objective of this project is to elucidate the duration and immune correlate of protection of non-specific epigenetic-mediated immune “innate training” by BCG against Covid19. To do so, we will evaluate transcription regulation (DNA methylation, ATAC-seq, Chromatin immunoprecipitation), gene expression (reverse transcription PCR, RNA-seq) and immune phenotyping experiments (ELISAs) and multi-parameter immune phenotyping. We have developed multiple flow cytometry panels to measure the immune response. DNA methylation EPIC and other sequencing based arrays allow for genome wide evaluation of

epigenetic silencing. Genome wide evaluation will be validated with site-specific evaluation using PCR as previously described (DiNardo et al JCI 2020; 32125282). Flow cytometry-based immune phenotyping allows 18 parameters to simultaneously be measured. By first stimulating the PBMCs with viral or mycobacterial peptides, we are able to simultaneously **measure and correlate** the quantity and quality of the viral and/ or mycobacterial induced immune phenotype (CD4, CD8, CD36, CD14, CD23), transcriptional changes (T-bet, GATA-3, Foxp3, Helios) and functional immune response such as cytokine release (IL-2, IL-4, IL-10, TGF- β , TNF and IFN- γ) or effector function (perforin, CD107a). COVID19-specific viral peptide mixes are in development and the PBMCs will be saved for a time when measuring COVID19-specific immunity is feasible.

i. Epigenomic DNA methylation

BCG induced non-specific immunity has been linked to chromatin conformation and DNA methylation. Therefore, these additional epigenetic studies will be evaluated as part of secondary analysis. The Illumina Infinium MethylEPIC array tests ~850,000 methylation sites including promoters, enhancers and non-island sites. Briefly, genomic DNA (gDNA) will be isolated (DNeasy protocol) from 1×10^6 PBMCs with >80% viability. From this quantity of PBMCs, I am able to retrieve >1.5 μ g DNA, which is sufficient to implement this assay (500ng). Experiments only proceed after strict quality control analyzing nucleic acid quality using a Qubit 3.0 fluorometer and Agilent 4200 Tape Station System. I will use the Zymo EZ DNA Methylation kit to bisulfite treat 500ng of gDNA prior to MethylEPIC testing. Methylation IDAT files will be imported into R statistical system using the Bioconductor (<http://www.bioconductor.org>) minfi package. After preprocessing and normalization, the Bioconductor limma package will identify probes with greater than 2 or less than 0.5-fold differential methylation with p-values < 0.05. Statistically significant differentially methylated probes will be visualized in Ingenuity Pathway Analysis. Gene ontology (GO) and Gene Set Enrichment Analysis analysis will be implemented using Molecular Signature Database (MSigDB) using hyper-geometric distribution that accounts for multiple comparisons. To evaluate if cell composition is confounding results and to determine the DNA methylation status of specific cell types (CD4, CD14, CD8, NK, and B cells), I will implement the bioinformatic pipelines EDEC (Epigenomic deconvolution) and MeDeCom (methylation decomposition). Both methods utilize linear algebra and classification techniques to quantify the DNA methylation profiles in several steps: 1) identifying optimal number of informative cell subpopulations 2) identify simultaneously both the estimated percentage of and the DNA methylation profile of each cell subpopulation. The explanatory cell subpopulations are then matched to DNA methylation profiles of known references via Spearman correlation. This approach offers multiple benefits: it enables us to assess DNA methylation changes in a cell type specific manner, but in a cost-effective approach because I will be profiling only the heterogeneous blood cells. Validation of bioinformatic EDEC results will then be carried out in magnetic bead purified cell types as described below.

j. ATAC-seq

DNA hyper-methylation inversely correlates with chromatin accessibility, however other means of epigenetic silencing exists (i.e H3K27me3, etc.). Therefore to confirm that specific DNA hyper-methylation marks correlate with decreased chromatin accessibility, we will implement ATAC-seq, epigenome-wide chromatin accessibility evaluation. 1×10^5 cells of interest (identified after EDEC as described above) undergo cell lysis, Tn5-mediated transposition followed by DNA purification, PCR amplification, DNA quality Bioanalysis (using Agilent and Qubit as described above) and sequencing. Bioconductor packages will be used for preprocessing, normalizing and identification of differential chromatin accessibility defined as greater than 2 or less than 0.5-fold difference with p values < 0.05.

k. Benefits and risks assessment, group relatedness

The risk to and burden for the subject of BCG vaccination is estimated to be low, according to two previous trials that have been performed with BCG vaccines.[7, 11, 13] The beneficial effect BCG vaccination for the individualized participant is unknown, although the objective is to prevent severe illness to SARS-CoV-2 infection. Using an adaptive design, the study aims to find a positive effect of BCG-vaccine on a population level, which could be applied quickly in participants allocated to placebo and implemented to hospitals that do not participate in the study.

11. STRUCTURED RISK ANALYSIS**a. Potential issues of concern**

An extensive description of the mechanisms of action of the BCG vaccine, referring to the available in vitro and in vivo evidence, could be found in the Summary of Product Characteristics and the Product Insert.

a. Level of knowledge about mechanism of action

BCG activates NOD2 receptor pathway, and subsequently induces long-term epigenetic changes in chromatin of myeloid cells.[10, 13] The epigenetic reprogramming leads to increased antimicrobial activity of myeloid cells (cytokine production, phagocytosis, reactive oxygen species release). At the same time, BCG induces potent activation of cellular specific immunity, with strong induction of Th1 responses and IFNg release.

b. Previous exposure of human beings with the test product

In a randomized controlled trial, healthy volunteers were vaccinated with placebo or BCG (Bacillus Calmette Guérin) vaccine. These volunteers were injected 14 days latter a trivalent influenza A vaccine. Volunteers previous vaccinated by BCG developed significantly greater titers against hemagglutinin A of the influenza A virus whereas their circulating monocytes were more potent for the production of IFNy.[28]

In another randomized placebo-controlled human challenge study, we found that BCG vaccination induced genome-wide epigenetic reprogramming of monocytes and protected against experimental infection with an attenuated yellow fever virus vaccine strain. Epigenetic reprogramming was accompanied by functional changes indicative of trained immunity.

In clinical studies followed by clinical endpoints, adolescents vaccinated with BCG have shown a 70% decrease in the incidence of respiratory tract infections compared to placebo.⁹ Consecutive BCG vaccination for 3 months in elderly individuals reduced the incidence of acute upper tract respiratory infections by 80% (95%CI=22-95%). BCG vaccine in immunocompetent adult people is considered safe, even in latently infected adults with prior infant BCG vaccination. In a randomized controlled trial that compared revaccination with BCG versus placebo, no serious adverse events were observed in the BCG arm.⁹

c. Can the primary or secondary mechanism be induced in animals and/or in ex-vivo human cell material?

No

d. Selectivity of the mechanism to target tissue in animals and/or human beings

The effect of BCG is restricted to immune cells, with no effects exerted in other tissues.

e. Analysis of potential effect

The effect of BCG on the susceptibility to / or severity of infection with SARS-CoV-2 is unknown. Previous clinical studies with BCG vaccination that have shown a reduction of respiratory tract infection between 30 to 70%. We hypothesize that BCG could alter the clinical course of SARS-CoV-2 infection and demonstrate 60% efficacy in preventing infection with SARS-CoV2. As mentioned previously, based on a previous trial, we expect rare serious adverse events.

f. Pharmacokinetic considerations

BCG is injected intradermally in the skin at the superior region of the arm, and it is known to persist at the site of injection for up to 4 weeks.

g. Study population

Health-care workers face an elevated risk of exposure to- and infection of- SARS-CoV-2.3. Of 75,465 laboratory-confirmed cases, 2,055 (2.7%) were reported among health care workers from 476 hospitals across China. The majority of cases (77.8%) were found in the working age (30–69 years).

h. Interaction with other products

No known interactions.

i. Predictability of effect

Multiple studies, among which randomized trials showed favorable *in vitro* and *in vivo* protective effects of BCG vaccination in the response to infections, among which viral infections. The objective of the trial is to evaluate if the same effect is observed when using BCG to improve the clinical course of SARS-CoV-2 infection. The safety profile of BCG vaccines has been studied extensively and no severe hazardous effects are expected.

j. Can effects be managed?

The beneficial effects of BCG will be straight forward to register. The local side-effects are minimal and easy to manage. Management of rare and serious adverse events (suppurative lymphadenitis, disseminated BCG and anaphylaxis) will occur by the study participant's primary medical provider in conjunction with expert advice from infectious disease physicians part of this study.

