3. STUDY DESIGN

A placebo-controlled multi-center adaptive randomized controlled trial, see figure 2 for the logistics of the study.

Figure 2: Study design of the trial

a. Duration of Follow-Up

The duration of follow-up for each participant depends on the interim results of the primary endpoint and the probability of obtaining a result, with a maximum of 168 days. The end of the study is defined as the last patient's last registration in the mobile application. Study participants will collect fingerstick dried blood spot (DBS) samples for serology testing at baseline, weeks 4, 8, 12, 16, 20 and 24. If they develop symptoms, they will be qPCR tested by nasopharyngeal swab, oral swab and/ or fecal swabs.

[figure not shown]

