e. Replacement of individual subjects after withdrawal

A participant will only be replaced in case of withdrawal before the administration of BCG vaccine/placebo.

a. Rationale:

A potential additional benefit of BCG vaccination is the impact of the vaccine on improving cognition and Alzheimer's Disease (AD) outcomes in the presence and absence of COVID19. There are series of published evidence that BCG can improve cognitive outcomes for AD and Parkinson's[16, 17]. Furthermore, there is mounting evidence that COVID-19 can impact the CNS[18-21], as evidenced by the loss of smell and taste reported by many patients as well as the presence of dementia in nearly 40% of patients. Prior pandemics have observed spikes in Parkinson's and other cognitive disorders afterwards[22] and coronaviruses have been associated with Parkinson's[23]. The cognition sub-study would involve cognition baseline and MRI (brain imaging) and follow up at 6 months and 2 years and would include BCG vaccinated, placebo-controlled, COVID-exposed and non-exposed groups. This study design will provide an extremely sensitive and longitudinal measure of cognitive ability that will allow examination of the impacts of COVID-19 and vaccination on the trajectory of mental status.

b. Premature termination of the study

During the study, interim analyses is planned. The safety and futility of the trial will be monitored carefully by the study team and DSMB during these interim analyses. If warranted, the study will be terminated (prematurely). Description of the DSMB and interim analysis is described further below.

8. OPTIONAL COGNITIVE SUB-STUDY (Not available at all sites).

a. Population:

400 subjects enrolled in main BADAS study.

b. Additional Inclusion Criteria:

- Normal or corrected-to-normal vision and hearing (able to see images on computer screen and hear auditory events delivered through the computer speaker).
- >45 years of age.

d. Additional Exclusion Criteria:

- Significant history of mental illness, drug or alcohol abuse; severe trauma preventing normal use of dominant hand (needed to move the mouse cursor); clinical depression (unless medically controlled); other neurologic conditions (i.e. stroke), or learning disability; ophthalmologic/visual problems that prevent viewing a computer screen at a normal distance (such as legal blindness, detached retinas, occlusive cataracts).

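### The efficacy stopping rule has no alpha adjustment: with 0.05 at each of three to six interims and at the final analysis, two-sided error is about 13–17%, not 5%

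*Combined protocol and SAP*

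**What the plan says.** - Section 10.a sets the design error rate: "with 80% power and 0.05 type 1 error in a two-tailed test". This is the only type 1 error given for the trial. The same section says the analysis will "report hazard ratios and p-values using Cox proportional hazard models" but does not say which Cox test (score, Wald or likelihood ratio) supplies the p-value.
- Section 10.b fixes only the first look: "One month after the first 100 participants are enrolled, an interim analysis will be held by the independent statistician of the trial". After that, "three to six interim analysis will occur based on temporal dynamics of enrollment as requested by the DSMB".
- Section 10.b makes these efficacy looks: "The above described statistical analysis will be evaluated as well as safety profile".
- The stopping rule in 10.b is: "We will stop the clinical trial early if the p-value of any interim analysis is smaller than the pre-specified type-1 error cutoff". The cutoff has no number. No boundary, spending function, level per look or level for the final analysis is given there or elsewhere.
- Section 7, under premature termination, describes the purpose of the same interims differently: "The safety and futility of the trial will be monitored carefully by the study team and DSMB during these interim analyses". Efficacy is not named.
- Section 3.a says that each participant's follow-up "depends on the interim results of the primary endpoint and the probability of obtaining a result", up to 168 days, without stating a rule.

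**The concern.** Each extra test of accumulating data gives chance another opportunity to cross a fixed cutoff. A rule that stops at the first p-value below 0.05, and otherwise tests the final data at 0.05, has an overall error well above 5%. A positive result from such a trial could not be read at the 0.05 level that the sample size was built on.

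The consequences are hard to reverse. Sections 1 and 10.k want a positive finding passed quickly to placebo participants and to hospitals outside the trial, and section 7.d provides for offering BCG to the placebo arm. Once placebo participants have received BCG, the randomised comparison cannot be recovered and no later analysis repairs the error rate.

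The early looks hold few events. Because the Cox test is not named, it is not even settled how small a split of cases could stop the trial.

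**Working it through.** **1. The plan's own figure.** Inputs from 10.a: 5% event rate (read as the placebo rate), relative risk 0.4 (so 2% on BCG), two-sided 0.05, 80% power, 700 per arm.

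n per arm = [1.96·√(2·0.035·0.965) + 0.842·√(0.05·0.95 + 0.02·0.98)]² / 0.03² = (0.509 + 0.218)² / 0.0009 ≈ 588

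The continuity-corrected figure is 653. The stated 700 is larger, and its power by the two-proportion formula is 86.4%. The 1400 is therefore not reproduced exactly, but it is on the safe side. It contains no stated allowance for interim looks.

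**2. Overall error with 0.05 at every analysis.** Under no effect, the statistics Z₁,…,Z_K are jointly normal with correlation √(t_j/t_k), where t is the fraction of information. The overall error is P(|Z_k| > 1.96 for at least one k). Equal spacing gives the following, by numerical recursion and confirmed by simulation of 2,000,000 trials for each K:

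| Analyses (interims + final) | Two-sided error | False benefit |
|---|---|---|
| 1 | 5.0% | 2.5% |
| 4 (3 + 1) | 12.6% | 6.3% |
| 5 (4 + 1) | 14.2% | 7.1% |
| 6 (5 + 1) | 15.5% | 7.7% |
| 7 (6 + 1) | 16.6% | 8.3% |

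**3. Other readings of the schedule.**
- Three to six includes the final analysis: 10.7–15.5%.
- The look after 100 participants is additional (5 to 8 analyses): 14.2–17.6%.
- Four analyses clustered late (information 0.7, 0.8, 0.9, 1): 9.0%.
- Four analyses early (0.02, 0.1, 0.3, 1): 16.3%.
- Seven front-loaded analyses: 21.7%.

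**4. Simulation closer to this trial.** 60,000 null trials were analysed by Cox partial likelihood. Assumptions: 1400 in total, uniform enrolment over 2 months, 168 days of follow-up, 5% incidence in both arms, first look at month 1.14 and final at month 7.52. Two-sided error:

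| Interims at month | Score | Wald | Likelihood ratio |
|---|---|---|---|
| 1.14, 2.5, 4 | 14.0% | 10.0% | 18.8% |
| 1.14, 2, 3, 4, 5, 6 | 17.5% | 12.9% | 22.4% |
| 1.14, 1.5, 2 | 13.8% | 7.5% | 19.6% |
| six between 1.14 and 2 | 16.2% | 8.4% | 22.6% |

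False benefit runs from 3.9% to 11.4% across these cases.

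**5. How few events could stop the trial.** With arms of equal size at risk:
- Score (log-rank): Z = (a − b)/√(a + b). A 4-to-0 split gives 4/√4 = 2.00, p ≈ 0.046.
- Likelihood ratio: 3-to-0 gives 2·3·ln 2 = 4.16 on 1 df, p ≈ 0.041.
- Wald: ln(a/b)/√(1/a + 1/b). It cannot reject with no events in one arm. 8-to-1 gives 2.079/1.061 = 1.96, p ≈ 0.0499.

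Under the step 4 assumptions the first look has a mean of 4.2 events, and the chance of a false stop there is 3.7% (score), 0.04% (Wald) or 9.0% (likelihood ratio). These first-look figures depend on fast enrolment: 1400/2 = 700 per month, so about 800 people are enrolled by month 1.14. If only the first 100 contribute 28 days each, the expected count is 100 × 28/168 × 0.035 to 0.05, or about 0.6 to 0.8 events, and that look adds almost nothing.

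**6. What control costs.** O'Brien-Fleming-type spending was applied to expected event fractions on the same four schedules, with score and Wald tests. Simulated type 1 error is 4.6–5.1%. At 5% v 2% the expected events are 700 × 0.05 + 700 × 0.02 = 49. Power is 84.9–87.8%, against 87.0% (Wald) and 87.8% (score) for a single analysis. Pocock-type spending gives 76.7–85.2%.

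**The case against.** The strongest reply is that 10.b calls its cutoff fixed in advance, so an adjusted value may exist, and inflation follows only if 0.05 is used each time. That condition is real and the percentages depend on it. It does not rescue the plan: if 0.05 is meant, error is inflated; if another value is meant, it is stated nowhere, so the rule can be neither applied nor audited.

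Second, 10.b does not describe equally spaced looks, so 13–17% is one scenario. This stands. The figure depends on timing and on the Cox test, and the pooled total is itself uncertain, because 10.a ties 1400 to one site while 10.b merges data from all sites. The direction is unaffected.

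Third, the first-look figures assume fast accrual; slower accrual would give fewer events. This also stands, and the main conclusion does not rest on them.

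Fourth, section 7 does not say that safety and futility are the only purposes of the interims, and sections 1 and 10.k show that acting early on efficacy was intended. The mismatch is a point to reconcile, secondary to the missing cutoff.

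Finally, 10.a reports on the first 500 participants, so the trigger for the first look may already have passed. Spending on observed events can absorb a look already taken, but the plan should record it.

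**Conclusion.** The concern holds. The documents define no cutoff for the repeated efficacy tests and no level for the final analysis. If 0.05 is used throughout with equally spaced looks, two-sided error is 12.6–16.6% instead of 5%, and false benefit 6.3–8.3% instead of 2.5%. Across the Cox simulations the two-sided figure is 7.5–22.6%. These sizes rest on 0.05 at each look, the assumed look times and, for the simulations, 1400 participants pooled, two-month enrolment and 5% incidence in both arms. Every case examined exceeds 5%. This must be corrected before an interim p-value is used to stop the trial.

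**What to change.** Replace the stopping sentence in 10.b with a boundary that holds overall two-sided error at 0.05 when the number of looks is not fixed:

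- Adopt an alpha-spending function, for example Lan-DeMets with O'Brien-Fleming-type spending, on observed over planned primary-endpoint events, and write out its exact form.
- State the planned number of events, which 10.a does not give.
- Name the Cox test used at every analysis.
- Set look times without reference to efficacy results, and record any look already taken with its event count.
- Test the final analysis at the remaining alpha.
- In 3.a, say that follow-up is shortened only if the boundary is crossed or the trial stops under its other stated rules.
- Reconcile the safety-and-futility wording in section 7 with the efficacy stop in 10.b.

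The change is to wording only and needs no extra participants. The worst simulated loss of power is from 87.0% to 84.9% (Wald, seven analyses), still above 80%. Other boundaries also control the error. A constant cutoff with equal spacing would have to be about p < 0.018 for four analyses or p < 0.013 for seven, but it needs the number of looks fixed in advance. Pocock-type spending falls below 80% power with seven analyses running to month 6.

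The real cost is a higher early hurdle. At about 55% of planned events, spending 2 − 2Φ(1.96/√t) on the total 0.05 puts the boundary at |Z| of about 2.65 (p about 0.008). Spending 0.025 separately on each side would put it near 2.81 (p about 0.005, ignoring earlier looks), which is why the form must be written down.
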